5.3 Dose Expansion Cohorts

Once the RP2D is reached, an additional 6-12 patients will be treated at this dose per arm. For a given arm, if all 3 dose cohorts are filled to 6 patients, then a 6 patient expansion will be added. If 2 or fewer dose cohorts are filled to 6 patients, then a 12 patient expansion will be added so that no more than 24 patients (dose escalation + expansion) will be treated on a given arm.

For the expansion cohort, patients will continue to be monitored for occurrence of DLT. If ≥ 2 of 6 patients experience DLT, the Principal Investigator will discuss with all study investigators and with CTEP whether further addition of patients is needed to re-assess the RP2D. Monitoring of all safety and toxicity data is done by the Principal Investigator and the Corresponding Organization on a real-time basis as data are entered into Medidata Rave using the Web Reporting Module. All participating sites are expected to notify the Principal Investigator when a DLT has occurred.

5.4 General Concomitant Medication and Supportive Care Guidelines

Growth factor support is not routinely recommended for low blood counts unless there is a concern for severe sepsis, septic shock or persistent infection (e.g. fungal infection) per institutional standards. Transfusion support is allowed, and can be used at the discretion of the investigators. Prophylactic antibiotics can be utilized as appropriate for disease or as needed in the post allo-HCT setting at the discretion of the investigators.

Suggested hypersensitivity precautions with ipilimumab: In the event of a hypersensitivity reaction, stop infusion, notify MD/NP/respiratory and pharmacy, administer oxygen as needed, monitor vital signs and proceed with administering hypersensitivity medications as needed. Medications to consider having available for hypersensitivity precautions:

Suggested medications for hypersensitivity precautions:

- Diphenhydramine 25-50mg IV as needed (begin with 25 mg, if continued reaction then administer additional 25 mg)
- Methylprednisolone or equivalent 40mg IV once as needed,
- Meperidine injection 12.5-25mg IV as needed for rigor/fever and/or chills during hypersensitivity reaction (start with 12.5 mg). If patient has continued reaction, administer additional 12.5 mg.
- Acetaminophen tablet 650 mg (oral) as needed for fever; hold if given already as a premedication
- Famotidine 20mg/50mL in NS IVPB or equivalent as needed for hypersensitivity; hold if already given as premedication
- Epinephrine IM injection 0.3mg as needed for anaphylaxis; may administer every 5 minutes up to 3 doses)
- Please refer to institution specific hypersensitivity reaction treatment algorithm for more clinical support

5.5 Duration of Therapy

Duration of therapy will depend on individual response, evidence of progression, and tolerance. In the absence of treatment delays due to adverse events, treatment (including priming, induction and maintenance) may continue for up to 12 cycles of combination therapy or until one of the following criteria applies:

- Disease progression (as defined by ELN 2017 criteria for AML and by IWG criteria for MDS). As T-cell infiltration of the tumor can look like progressive disease, please

discuss the results of radiographic assessments (for extramedullary disease) showing progressive disease with the overall PI before removing a patient from the study for disease progression.

- Intercurrent illness that prevents further administration of treatment,
- Unacceptable adverse event(s) requiring permanent stopping of both ipilimumab and decitabine
- Patient decides to withdraw from the study
- Pregnancy
 - All women of child bearing potential should be instructed to contact the investigator immediately if they suspect they might be pregnant (e.g., missed or late menstrual period) at any time during study participation.
 - The investigator must immediately notify CTEP in the event of a confirmed pregnancy in a patient participating in the study.
- General or specific changes in the patient's condition render the patient unacceptable for further treatment in the judgment of the investigator.
- Termination of the study by sponsor.

Ipilimumab is expected to trigger immune-mediated responses, which require activation of the immune system prior to the observation of clinical responses. Such immune activation may take weeks to months to be evident. For patients with a mass, some patients may have objective volume increase of tumor lesions or other disease parameters (based on study indication, i.e., hematologic malignancies) within (specific 12-24) weeks following the start of ipilimumab dosing. Such patients may not have had sufficient time to develop the required immune activation or, in some patients, tumor volume or other disease parameter increases may represent infiltration of lymphocytes into the original tumor or blood. In conventional studies, such tumor volume or relevant laboratory parameter increases during the first 12 weeks of the study would constitute disease progression and lead to discontinuation of imaging to detect response, thus disregarding the potential for subsequent immune-mediated clinical response. For the purposes of this clinical trial with AML and MDS, patients with sole extramedullary disease with evidence of tumor progression by PET imaging at the end of cycle 2 but without rapid clinical deterioration or change in performance status who do not require additional immediate therapy, may continue to be treated with ipilimumab and clinically observed until the next response evaluation (in this scenario, would then consider repeating a PET scan at the end of cycle 2) to allow detection of a subsequent tumor response.

The reason(s) for protocol therapy discontinuation, the reason(s) for study removal, and the corresponding dates must be documented in the Case Report Form (CRF).

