Evidence for anti-leukemic activity in the absence of graft versus host reactivity with CTLA-4 blockade was previously studied in a mouse model of minor histocompatibility-mismatched bone marrow transplantation [62]. In a mouse model of minor histocompatibility mismatched bone marrow transplantation, delayed CTLA-4 blockade induced anti-leukemic activity in the absence of graft versus host reactivity [62]. A pilot study next demonstrated safety with low-dose ipilimumab in the treatment of patients with relapsed hematologic malignancies post alloHCT [5]. Results from this study suggested that titration of ipilimumab might be possible in order to generate a graft-versus-tumor response. Pharmacokinetic data generated from this pilot study demonstrated that higher doses of ipilimumab correlated with increased ipilimumab exposure and that those doses may be sufficient to saturate CTLA-4 binding sites [5]. A Dana-Farber Cancer Institute led Phase I/Ib multi-center study (NCT01822509) of dose-escalated ipilimumab in the post-transplant setting for relapsed hematologic malignancies demonstrated substantial anti-tumor activity [4, 63]. There was no formal clinical response for patients treated in the 3 mg/kg cohort. Out of 6 evaluable patients in the 3 mg/kg cohort, one patient had chronic GVHD of the liver, which was the only DLT in the cohort. There was evidence of immune-related adverse events in two patients (1 patient with grade 2 pneumonitis and 1 patient with grade 2 diarrhea), which rapidly reversed with glucocorticoids and did not prevent further administration of ipilimumab. Twenty-two patients including an expansion cohort went on to receive 10 mg/kg dosing of ipilimumab. The overall response rate (ORR) in the 10 mg/kg dose cohort was 32% (7/22) although 59% (13/22) had disease reduction. Responders included 5 with AML, 1 partial response (PR) with classical Hodgkin's, and 1 PR with multiple myeloma with highly refractory lung plasmacytoma. Of the AML patients treated on study, 42% (5 of 12) achieved complete remission (CR), including 3 with extramedullary AML, 1 with myeloid sarcoma and 1 with smoldering MDS/AML with marrow involvement (low blast burden). Importantly, responses have been durable in three of the AML responders, ranging from 12-16 months. The median duration of response has not yet been reached. The 1 year OS was 49% at 15 months [4]. Exploratory correlative studies revealed a decrease in the ratio of T_{reg}/T_{conv} ratio, suggesting possible augmentation of the graft versus tumor effect. Results from this phase I/Ib study suggest that ipilimumab is feasible for relapsed disease after allo-HCT although at the dose of 10 mg/kg there was evidence of both immune related adverse events and GVHD, which were distinguished by biopsy. In the 10 mg/kg cohort, there was evidence of dose-limiting toxic effects including 2 patients with chronic GVHD of the liver and 1 patient with grade II acute GVHD of the gut. These GVHD cases resolved with steroids but precluded further administration of ipilimumab. Immune-related adverse events were observed in 3 patients (1 patient with grade 2 immune thrombocytopenia; 1 patient with grade 3 colitis; 1 patient with grade 2 pneumonitis and 1 patient with grade 4 pneumonitis). With steroid treatment, ipilimumab was resumed ~ 3 weeks in 2 patients. One of these patients died 42 days after receiving initial ipilimumab (grade 3 colitis and grade 4 pneumonitis). Notably, no infectious complications were seen that were grade 3 or higher. Consequently, the trial is now investigating the safety and preliminary efficacy

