 - In the absence of disease, patients must have an absolute neutrophil count $\geq 500 \times 10^9 / L$ or platelet count to $\geq 25,000 \times 10^9 / L$ to proceed.
 - Hematologic criteria to start cycle 4:
 - If there is persistent disease (e.g. peripheral blasts, any marrow disease, persistent leukemia cutis or other form of extramedullary

disease), then there are no hematologic requirements to start cycle .

- In the absence of disease, patients must have an absolute neutrophil count $\geq 500 \times 10^9/L$ or platelet count to $\geq 25,000 \times 10^9/L$ to proceed; otherwise administration of treatment will be delayed.

- **Treatment**

- Decitabine 20 mg/m² IV daily over 60 minutes (+/- 15 minutes) x 5 consecutive doses on **days 1-5** every 4 weeks given per institutional guidelines
 - **Pre-medication prior to chemotherapy:** per institutional standards
- Ipilimumab IV (per dose level as in table above) on **day 1** over 90 minutes (+/- 15 minutes) every 4 weeks for a total of 4 doses during induction
 - Dose escalation levels: 3 mg/kg (**starting dose**, dose level 0), 5 mg/kg (dose level 1), and 10 mg/kg (dose level 2)
 - Dose de-escalation level: 1 mg/kg
- Decitabine will be dosed prior to ipilimumab on day 1
- Vitals signs will be repeated hourly from time of ipilimumab infusion for up to two hours after infusion ends (+/- 30 minutes) on day 1 after first dose and up to one hour after infusion ends (+/- 30 minutes) on day 1 for subsequent doses.

- Clinic visits (including physical exam, medication review, ECOG and AE review)
 - Cycle 1: on day 1 and day 15 (+/- 3 days)
 - Cycles 2-4: on day 1 (+/- 3 days).

- **Procedures:**

- Labs
 - Cycle 1: on day 1, day 15 (+/- 3 days).
 - Cycles 2-4: on day 1 (+/- 3 days).
 - End of cycles 1, 2 and 4 on day of bone marrow biopsy (on a day between days 24-28).
- Bone marrow biopsy (including aspirate (if aspirable), core, flow cytometry, cytogenetics) will be at the end of cycles 1, 2 and 4 (on a day between days 24-28) for response assessment.
- If sole extramedullary disease (unless leukemia cutis), routine evaluation may include PET imaging (if FDG avid at time of diagnosis) at the end of cycles 2 and 4 (on a day between days 24-28) for response assessment.

- **Correlative studies:** peripheral blood and aspirate collection at the end of cycles 1, 2 and 4 on a day between days 24-28 (see correlative calendar in [section 10.2](#)).

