c: Albumin, alkaline phosphatase, total bilirubin, bicarbonate, BUN, calcium, chloride, creatinine, glucose, potassium, total protein, SGOT [AST], SGPT [ALT], sodium, uric acid, magnesium, phosphorus.

d: Every 3 months unless clinically indicated: gamma-GT, direct bilirubin, LDH, TSH, and lipase

e: Please see [Appendix F](#) for helpful study check list including immune related AE evaluation

f: PET scans are required only for those with sole extramedullary disease (no marrow involvement by morphology) and optional for those with extramedullary and marrow involved AML. PET scans are standard imaging tests for those with extramedullary disease involvement. Study can be performed any time between day 24-28 at the end of cycles 2 and 4 (suggested time frame). However as clinical scenario may vary with patients with sole extramedullary disease, we will allow imaging window of +/- 4 weeks based on clinical scenario or scheduling logistics. Please send report and imaging (on CD) with redacted PHI for central review of extramedullary AML events to Attn: [name], Research Project Manager for CTEP 10026; Dana-Farber Cancer Institute; [name]. If there are reports only, please fax to [contact] or email to: [contact]

g: If patient has sole extramedullary disease and there was no resolution of FDG-avid disease by the end of cycle 2, then patients should have a repeat PET at the end of cycle 4 per standard of care. Study can be performed any time between day 24-28 at the end of cycles 2 and 4 (suggested time frame). However as clinical scenario may vary with patients with sole extramedullary disease, we will allow imaging window of +/- 4 weeks based on clinical scenario or scheduling logistics. Please send report and imaging (on CD) with redacted PHI for central review of extramedullary AML events to Attn: [name], Research Project Manager for

CTEP 10026; Dana-Farber Cancer Institute; [name]. If there are reports only, please fax to [contact] or email to: [contact]

- h: Serum pregnancy test (women of childbearing potential).- Negative results required within 72 hours of treatment start

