- n: For those with known HIV they must get a CD4 count and an HIV viral load (PCR).
- o: Baseline echocardiogram and EKG required for screening (if done within 4 weeks of treatment start does not need to repeat unless there is a clinical concern) and at any other time that is clinically indicated during the trial as it relates to footnote q
- p: Peripheral blood, aspirate, core biopsy, or FFPE to be collected per schedule described correlative table below.
- q: Alert PI if there is concern for cardiac toxicity (minimum assessment: cardiology consult, EKG, echocardiogram, and labs CPK and troponin; refer to section 6.4.7)
- r: Please see section 7.3.5 of the protocol for reporting requirements for GVHD and suspected immune related AEs to enable central review
- s: MUGA scan is a suitable alternative to an echocardiogram
- t: For participants enrolled on Arm A (post transplant), a formal GVHD assessment is required at minimum on Day 1 of each cycle utilizing the GVHD assessment worksheet provided in Appendix B

	Maintenance cycles and end of study										
	C5 D1 ^b	C6 D1 ^b	C7 D1 ^b	C7 D24 ^a	C8 D1 ^b	C9 D1 ^b	C10 D1 ^b	C10 D24 ^a	C11 D1 ^b	C12 D1 ^b	End of study ^{i,j}
Ipilimumab^A	X		X			X			X		
Decitabine^B	X	X	X		X	X	X		X	X	
Concurrent meds	X	X	X		X	X	X		X	X	
Physical Exam	X	X	X		X	X	X		X	X	X ^k
Vital signs	X	X	X		X	X	X		X	X	
Height	X										
Weight	X	X	X		X	X	X		X	X	
Performance status	X	X	X		X	X	X		X	X	
CBC w/diff, plts	X	X	X	X	X	X	X	X	X	X	X
Serum chemistry^c	X	X	X		X	X	X		X	X	X
Immune-related labs^d			X				X				X
Adverse event evaluation^{e,f,m}	X	X	X		X	X	X		X	X	X ^k
GVHD Assessment	X	X	X		X	X	X		X	X	X
Bone marrow^f				X ^f				X			X ^f
T cell chimerism^g											X
Correlative studies^h				X				X			X

A: Ipilimumab: Dose as assigned by dose level. Administered every 8 weeks. Dosed per weight on day 1 of a cycle.
B: Decitabine: 20 mg/m² daily IV for 5 consecutive days on days 1-5. Dosed per weight on day 1 of the lead in
a: Can be done any time between day 24-28
b: +/- 3 days
c: Albumin, alkaline phosphatase, total bilirubin, bicarbonate, BUN, calcium, chloride, creatinine, glucose, potassium, total protein, SGOT [AST], SGPT [ALT], sodium, uric acid, magnesium, phosphorus.
d: At baseline, C1D1, and then every 3 cycles thereafter or more frequently when clinically indicated: gamma-GT, direct bilirubin, LDH, TSH, and lipase
e: Please see [Appendix F](#) for helpful study check list including immune related AE evaluation

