11. MEASUREMENT OF EFFECT

Although the clinical benefit of combination ipilimumab and decitabine has not yet been established, the intent of offering this treatment is to provide a possible therapeutic benefit, and thus the patient will be carefully monitored for tumor response and symptom relief in addition to safety and tolerability. Patients with MDS/AML will be assessed by standard criteria. For the purposes of this study, patients should be re-evaluated at the end of cycles 1, 2 and 4, and then every 3 cycles on treatment, and then at time of suspected relapse if relevant. The aspirate sample collected at the end of cycle 1 is for correlative research only. In addition to a baseline PET scan (for those with extramedullary disease, not required for those with leukemia cutis only), follow-up response scans will also be obtained at the end of four cycles of combination therapy following initial documentation of an objective response.

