11.1.2 Progression-Free Survival

Overall Survival: Overall Survival (OS) is defined as the time from time of registration to death due to any cause, or censored at date last known alive. We will evaluate for survival differences among patients that respond based on transplant status.

Progression-Free Survival: Progression-Free Survival (PFS) is defined as the time from time of registration to the earlier of progression or death due to any cause. Participants alive without disease progression are censored at date of last disease evaluation.

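### For patients with sole extramedullary disease the PET rules disagree, and after cycle 4 PFS and remission duration can run on a marrow that never showed the disease

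*Combined protocol and SAP*

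**What the plan says.** The imaging rules for sole extramedullary disease stand in four sections of the protocol.

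- **Section 5.1, induction.** Leukemia cutis aside, "routine evaluation may include PET imaging (if FDG avid at time of diagnosis) at the end of cycles 2 and 4".
- **Section 10.1, calendar.** PET is marked before study, at the end of cycle 2 and at the end of cycle 4. Footnote f says "PET scans are required only for those with sole extramedullary disease (no marrow involvement by morphology"), without an FDG-avidity condition or a leukemia cutis exemption, and allows a window of +/- 4 weeks. Footnote g, attached to the cycle-4 cell, applies "If patient has sole extramedullary disease and there was no resolution of FDG-avid disease by the end of cycle 2" and asks for a repeat scan at the end of cycle 4.
- **Section 11.** "follow-up response scans will also be obtained at the end of four cycles of combination therapy following initial documentation of an objective response".
- **Section 5.5.** A clinically stable patient with PET progression at the end of cycle 2 may continue until the next response evaluation. The same sentence says the team "would then consider repeating a PET scan at the end of cycle 2".

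The second calendar table, "Maintenance cycles and end of study", lists marrow at the end of cycles 7 and 10 and at end of study, with blood count and physical exam on day 1 of each cycle. It has no PET row and no skin biopsy row. The maintenance text in Section 5.1 agrees.

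For analysis, Section 11.1.2 says "Participants alive without disease progression are censored at date of last disease evaluation" and does not say which kind of evaluation counts. Section 11.1.1 runs response duration to the first objectively documented recurrence or progression and gives no censoring date.

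**The concern.** By footnote f, these patients have no marrow involvement on morphology. A normal marrow therefore says little about the site where they have disease. If it counts as a disease evaluation, each one adds progression-free time and leaves remission duration running, although nobody has imaged or biopsied the lesion. Section 1.2 lists 1-year PFS and duration of remission as secondary objectives.

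The induction rules matter for a different reason. Sites that read them differently will scan different patients at cycle 4, so response and progression would not be ascertained alike across the trial.

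The protocol has grounds to expect activity outside the marrow. Section 2.4 reports five complete remissions among AML patients in the cited post-transplant ipilimumab study, "including 3 with extramedullary AML, 1 with myeloid sarcoma".

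**Working it through.** No stated figure in the plan bears on this point, so the check is a comparison of rules followed by calendar arithmetic.

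**1. The rules side by side**

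| Question | Places | Result |
|---|---|---|
| Is PET required? | 5.1: optional, if FDG avid, cutis exempt. Footnote f: required, neither limit stated | Conflict |
| What triggers the cycle-4 scan? | Footnote g: no resolution at cycle 2. Section 11: a documented objective response | Different triggers |
| When is the scan repeated after PET progression at cycle 2? | 5.5: end of cycle 2, although the patient is being observed to the next evaluation | Cannot be done as written |

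**2. Time without a scheduled PET**

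Inputs: 28-day cycles and a one-cycle lead-in (Section 5.1), and up to 12 combination cycles (Section 5.5). Weeks from lead-in day 1 to the end of combination cycle c = 4 × (1 + c).

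- Last calendar PET, end of cycle 4: 4 × 5 = week 20.
- Marrows, end of cycles 7, 10 and 12: weeks 32, 44 and 52.
- Gap: 52 − 20 = 32 weeks, or 32/52 = 62% of the period.
- With the cycle-4 PET taken 4 weeks late: 52 − 24 = 28 weeks.
- In days: cycle 4 day 24–28 falls 135–139 days after lead-in day 1, and cycle 12 day 24–28 falls 359–363 days after. The difference is 224 days, or 32 weeks.

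Section 5.5 speaks of apparent growth 12 to 24 weeks after ipilimumab starts. Counted from first ipilimumab, the end of cycle 4 is week 4 × 4 = 16, or week 20 with the late window. Scheduled imaging therefore ends inside that period.

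**3. What finds disease in the gap**

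Physical exam can find leukemia cutis or a palpable mass. For other sites nothing scheduled looks. Under Section 11.1, concern about progression prompts a marrow, and no imaging is named.

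**4. Effect on the endpoint**

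Take a patient with a week-20 PET who completes treatment with clean marrows. Read literally, Section 11.1.2 can censor that patient at about week 52. If the involved site must have been evaluated, the censoring date is week 20 or the last documented exam able to show the lesion. The two dates can differ by up to 32 weeks.

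**5. Size per patient**

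The plan does not say how many such patients are expected. If no one is censored before one year, one patient wrongly counted as progression-free moves 1-year PFS by 1/12 = 8.3 points or 1/18 = 5.6 points. These are the two sizes at the MTD/RP2D in Section 13.1. For a full arm of 24 the step is 1/24 = 4.2 points. With censoring the Kaplan-Meier step is not fixed.

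**The case against.** The case for leaving the plan alone is substantial.

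- The calendar already marks PET at the end of cycles 2 and 4, and footnote f names the same visits. Neither footnote g nor Section 11 says that its trigger is the only one. Together they can cover non-resolvers and responders. A reader might infer that an unresolved patient gets no cycle-4 scan under Section 11, but Section 11 withdraws nothing from the calendar.
- The wrong visit in Section 5.5 is an evident slip, and the sentence is permissive.
- Section 11 could mean four cycles after the response. For a response at the end of cycle 2 that is the end of cycle 6 (week 28), leaving 24 weeks. For a response at the end of cycle 4 it is the end of cycle 8 (week 36), leaving 16 weeks. The calendar shows no such scan, however, and it would cover responders only.
- A reader might infer that these patients are judged on marrow alone. The documents do not support that. Appendix D denies complete remission while extramedullary disease remains and counts its return as relapse. Appendix H also counts extramedullary relapse. Section 10.2 lists extramedullary tissue at end of treatment or suspected relapse, and Section 5.5 foresees radiographic progression.
- The remissions in Section 2.4 came from single-agent treatment after transplant and are not described as sole extramedullary disease. They do not size this subgroup, which could be empty.

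These points limit the concern but do not remove it. The criteria cover extramedullary disease, but in maintenance no scheduled imaging or biopsy supplies the information. That a clean marrow counts as the last disease evaluation is a permitted reading of Section 11.1.2, not something it states.

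**Conclusion.** The point holds in a limited form. The PET rules are inconsistent in three respects and need reconciling. After cycle 4, extramedullary relapse or progression that is neither visible nor palpable has no scheduled test for about 32 weeks, or 28 with the full window. The censoring rule lets a marrow stand in for the missing look.

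The 32 weeks assume that the cycle-4 PET is done on time, Section 11 adds no later scan, and the patient completes all 12 cycles. A patient who stops sooner has a shorter gap.

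A reader might also infer that a missed late relapse distorts the response rate. It does not, because Section 11.1 uses the best response recorded up to progression. The exposed quantities are PFS and remission duration, which are secondary and summarised by Kaplan-Meier. The MTD/RP2D rests on toxicity in the first 8 weeks of combination and is unaffected. The total effect cannot be sized, because the number of these patients is not given.

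**What to change.** 1. **One assessment rule.** Reconcile Section 5.1, Section 5.5, footnotes f and g in Section 10.1, and Section 11 into one rule consistent with the calendar's scans at the end of cycles 2 and 4. It should state who is scanned, whether the scan is required, and how non-avid disease and leukemia cutis are handled. Correct the repeat scan in Section 5.5 to the next response evaluation, which that sentence already names.
2. **One analysis rule.** In Sections 11.1.1 and 11.1.2, state that for sole extramedullary disease the last disease evaluation must include the involved site, by imaging, biopsy, or documented exam where disease is visible or palpable. A marrow alone does not extend PFS or response duration. Report a sensitivity analysis that uses the date of any evaluation.

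The first change is wording in four sections. The second is analysis only and adds no procedure. Its cost is earlier censoring for a few patients. There may also be an asymmetry when later progression is found by unscheduled work-up: events count whenever found, while event-free time stops at the last look at the site. The sensitivity analysis would show how much that matters.

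Replacing the maintenance marrow with PET is not advised on this ground. It would open a blind spot for marrow relapse and lose the aspirates planned in Section 10.2. Whether to add imaging in maintenance is for the sponsor. Nothing here bears on whether a patient should continue treatment after PET progression.
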